11.9.3 Physical Examination

A complete physical examination will be performed at screening and study exit. A complete physical examination includes assessments of the following: head, eyes, ears, nose, throat (HEENT), neck, chest, lungs, abdomen, musculoskeletal, dermatological, cardiovascular/peripheral vascular, and general neurological examination.

A brief physical examination will be done on Day -1, Day 3 (48 hours post-start of infusion), Day 8 ± 1 , and Day 15 ± 1 , and as directed by symptoms.

A brief physical examination includes assessments of the following: HEENT, chest, lungs, abdomen, dermatological, cardiovascular/peripheral vascular, and areas of note elicited from the subject.

11.9.4 Drug and Alcohol Screen

A urine drug screen (amphetamines, methamphetamines, barbiturates, benzodiazepines, tetrahydrocannabinol, cocaine, opiates, PCP, MDMA, methadone) and an alcohol breath test will be performed at screening and at admission on Day -1.

11.9.5 Sheehan Suicidality Tracking Scale (S-STS)

The S-STS will be performed at screening and study exit. The S-STS is a prospective, patient self-reported or clinician administered rating scale that contains 16 questions to track both treatment-emergent suicidal ideation and behaviors.^{4,5}

This scale will be clinician administered, completed on site, and will be in paper format. The source document will be provided by the Sponsor. The assessment period for completing the scale will be lifetime look back prior to screening for the assessment at the screening visit and since screening for the assessment at the study exit visit.

If the Investigator determines that a subject is at risk of suicide or self-harm, appropriate measures to ensure the subject's safety and obtain mental health evaluation must be implemented. The subject must immediately be discontinued from the study. The event should be recorded as either an AE or a serious AE (SAE) as determind by the Investigator and reported within 24 hours to the Sponsor.

11.9.6 Laboratory Assessments

11.9.6.1 Hematology

Hematology will be performed at screening and study exit.

Hematology will also be performed on Day -1, Day 3 (approximately 48 hours post-start of infusion), and Days 8 ± 1 , 15 ± 1 , and 29 ± 2 .

The following will be assessed: complete blood count with differential, hemoglobin, and hematocrit.

11.9.6.2 Biochemistry

Biochemistry will be performed at screening and study exit.

Biochemistry will also be performed on Day -1, Day 3 (approximately 48 hours post-start of infusion), and Days 8 ± 1 , 15 ± 1 , and 29 ± 2 .

The following will be assessed: albumin, alkaline phosphatase, AST, ALT, urea, calcium, chloride, glucose, phosphorus, potassium, creatinine, sodium, total bilirubin, total protein, total cholesterol, HDL, LDL, and triglycerides.

11.9.6.3 Coagulation

Coagulation will be performed at screening and study exit.

Coagulation will also be performed on Day -1, Day 3 (approximately 48 hours post-start of infusion), and Days 8±1, 15±1, and 29±2.

The following will be assessed: prothrombin time (PT)/ international normalized ratio (INR) and activated partial thromboplastin time (aPTT).

11.9.6.4 **Serology**

Serology will be performed at screening. The following will be assessed: HIV antigen and antibody, hepatitis B surface antigen (HBsAg), and hepatitis C virus (HCV) antibody.

11.9.6.5 Urinalysis

Urinalysis will be performed at screening and at study exit.

Urinalysis will also be performed on Day -1, Day 3 (approximately 48 hours post-start of infusion), and Days 8 ± 1 , 15 ± 1 , and 29 ± 2 .

The following will be assessed: macroscopic examination, pH, specific gravity, protein, glucose, ketones, bilirubin, occult blood, nitrite, urobilinogen, and leukocytes. Unless otherwise specified, microscopic examination will be performed according to internal procedures.

11.9.7 Injection Site evaluation

Skin reactions at the injection site will be recorded prior to start of study drug infusion and approximately 0.5, 1, 24 (Day 2), 48 (Day 3), 96 (Day 5±1) and 168 (Day 8±1) hours post-start of infusion.

A trained observer, whom is blinded to the randomization scheme, will check and record local dermal reaction at the application site using the rating scale in Table 13. When possible, the same evaluator will follow the subject through the study. In the event that more than one evaluator is required to follow the subject through the study, every precaution should be taken to limit the number of evaluators.

Table 13. Injection Site Reaction Scores

None	0	No reaction
Mild	1	Easily tolerated erythema and/or light bruising and/or mild pain
Moderate	2	Distributing erythema with swelling and/or distributing bruising and/or distributing pain
Severe	3	Almost intolerable symptoms, or clinically definite skin necrosis, characterized by any of the following: oozing, weeping, skin breakdown, ulceration, scar formation

In addition, bleeding or fluid loss at the injection site will be documented. The diameter of any erythema, swelling or induration will be measured (mm) in two dimensions.

Reactions < 10 mm will not be listed as an AE unless it persists for more than 24 hours.

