5.4.3 Rationale for the Study Population

A male healthy volunteer population has been selected for the study because healthy subjects with no concomitant diseases and using no concomitant medications represent a homogenous population allowing for proper evaluation of the safety, tolerability, and PK of a drug without confounding factors.

No reproductive studies have been conducted in NS101. Since risks to a developing foetus or reproductive effects are not known, only male subjects will be included in the study. Furthermore, non-vasectomized male subjects with a female partner of childbearing potential will be required to use an appropriate method of contraception, and will be restricted from sperm donation.

6. Objectives

Primary objective:

To assess the safety and tolerability of NS101 following IV administration of single ascending doses in healthy subjects.

Secondary objectives:

- To characterize the PK profile of NS101 in serum and NS101 concentrations in CSF following single IV infusion doses in healthy subjects.
- To characterize the PD profile of NS101 through FAM19A5 in plasma and FAM19A5 concentrations in CSF following single IV infusion doses in healthy subjects.
- To evaluate the immunogenicity profile of NS101.

7. Study Endpoints

Primary endpoints:

- Incidence, nature, relatedness, and severity of AEs.
- Changes in vital signs measurements, physical examination, clinical laboratory test findings, 12-lead-ECG.

Secondary endpoints:

- Serum PK parameters for NS101 will include: AUC_{0-24} , AUC_{0-t} , AUC_{inf} , C_{max} , T_{max} , $T_{\frac{1}{2}}$ el, K_{el} , Cl, and V_z .
- Concentrations of NS101 in CSF.
- Serum to CSF ratio of NS101 concentrations.
- Immunogenicity of NS101, measured as the number and percentage of subjects who develop detectable ADAs and NAbs.

[figure not shown]
Exploratory endpoints:

- Effect (E): variation of level of FAM19A5 (Δ FAM19A5) following administration of NS101:
 - o PD: Change in baseline of FAM19A5 levels
 - o PD parameters in plasma: AUEC_{0-t}, E_{max} , and TE_{max} .
 - o Concentrations of FAM19A5 in CSF.

8. Study Design

This will be a single center, Phase 1, double-blind, randomized, placebo-controlled, sequential SAD study (Figure 9). The study will consist of **8** cohorts (Cohorts 1 to **8**).

Figure 9. Study Diagram

8.1 Design for Cohorts 1 to 8

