11.14 Adverse Events

11.14.1 Definition of Adverse Event

An AE is defined as any untoward medical occurrence in a patient or clinical trial subject administered a pharmaceutical product and which does not necessarily have a causal relationship with the treatment. An AE can, therefore, be any unfavorable and unintended sign (including an abnormal laboratory finding, for example), symptom, or disease temporally associated with the use of a medicinal (investigational) product, whether or not considered related to the medicinal (investigational) product.

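### Small, short-lived injection-site reactions are exempt from AE listing whatever their severity score, so some moderate or symptomatic severe reactions miss the primary AE summaries

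*Protocol*

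**What the plan says.** Protocol 11.9.7 has a blinded observer score the infusion site on the scale in its Table 13. Score 2 reads "Distributing erythema with swelling and/or distributing bruising and/or distributing pain". Score 3 reads "Almost intolerable symptoms, or clinically definite skin necrosis, characterized by any of the following: oozing, weeping, skin breakdown, ulceration, scar formation". Neither score has a size threshold. The section then says what is sized: "The diameter of any erythema, swelling or induration will be measured (mm) in two dimensions". The listing rule follows: "Reactions < 10 mm will not be listed as an AE unless it persists for more than 24 hours". Duration is its only exception; the score plays no part. Site checks are made before the infusion, at "approximately 0.5, 1, 24 (Day 2), 48 (Day 3") and again at 96 and 168 hours.

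Protocol 11.14.1 defines an AE broadly. It includes "any unfavorable and unintended sign", as well as symptoms and disease, with no limit on size or duration. SAP 11.2 repeats the definition in similar words.

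The first primary endpoint (Protocol section 7, SAP section 4) is "Incidence, nature, relatedness, and severity of AEs". SAP 11.2 builds every AE summary from treatment-emergent AEs. SAP 11.9 tabulates and lists the site scores separately, and SAP section 4 does not name that table as an endpoint.

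**The concern.** The exemption was presumably meant to keep trivial cannula marks out of the AE listing. As worded, it also removes reactions that the observer has scored as moderate, or as severe on symptoms, provided that they are small and brief. Two people following the protocol could record the same event differently, one by 11.9.7 and the other by 11.14.1.

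The AE summary is the main safety output of this first-in-human study, and Protocol 5.4.1 names local skin reactions at the site among the possible manifestations of an antibody infusion reaction. The rule therefore filters a kind of event that the protocol anticipates. Relationship to study drug (Protocol 11.14.4), CTCAE grade (11.14.3) and coding by organ class and preferred term (SAP 11.2) are planned only for AEs. A reaction kept off the AE list gets none of them.

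**Working it through.** The plan gives no reaction rate and no figure for this point, so there is nothing to reproduce. The check sets the passages side by side and then does some simple arithmetic.

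**Step 1. Apply both rules to each kind of reaction.**

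| Reaction | Under 11.9.7 | Under 11.14.1 |
|---|---|---|
| Score 1, measured < 10 mm, 24 h or less | Not listed | AE on a literal reading |
| Score 2, measured < 10 mm, 24 h or less | Not listed | AE |
| Score 3 on symptoms, measured < 10 mm, 24 h or less | Not listed | AE |
| Score 3 on skin damage, < 10 mm | Listed, if it outlasts 24 h as would be expected | AE |
| Pain or bruising alone, no diameter taken | Unclear | AE |
| Any score, 10 mm or more | Exemption does not apply | AE |

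The rules conflict in the first three rows. The second and third matter most, because there the protocol's own scale calls the event moderate or severe. The fifth row is an ambiguity: only three kinds of skin change are measured in millimetres, and the rule does not say what happens to a reaction without a measurement.

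**Step 2. Look for a route back into the AE data.** SAP 11.6 turns an abnormal examination finding after dosing into an AE if it is judged a clinically significant change. The scheduled post-dose examinations (Protocol 11.9.3) are on Day 3 (48 h), Days 8 and 15 and at study exit, with others as symptoms direct. A reaction that clears within 24 hours is over before the first scheduled one, so this route depends on a symptom-directed examination. SAP 11.9 reports the score but does not feed the AE tables.

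**Step 3. Duration against the nominal checks.** A reaction first seen at 0.5 h and still present at 24 h has been observed for 24 − 0.5 = 23.5 h. One first seen at 1 h has been observed for 24 − 1 = 23 h. Both fall just short of the rule's threshold, so on scheduled checks alone persistence is shown only at 48 h.

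**Step 4. Effect of one excluded subject.** Each dose has 6 active subjects (Protocol 8.1, SAP 3.3). One exclusion lowers that dose's site-reaction AE incidence by 1/6 = 16.7 percentage points, and two lower it by 2/6 = 33.3. Placebo is pooled over 8 cohorts of 2 (SAP 6.1), so one exclusion there is 1/16 = 6.25 points. Overall AE incidence moves by these amounts only if the excluded subject has no other treatment-emergent AE.

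**Step 5. Illustration with assumed rates.** Let p be the chance that an active subject has a site reaction and q the share of reactions that the rule removes. The chance that a dose group shows at least one site-reaction AE is 1 − (1 − p(1 − q))^6.

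| p | q = 0 | q = 0.25 | q = 0.5 | q = 0.75 |
|---|---|---|---|---|
| 0.10 | 0.469 | 0.374 | 0.265 | 0.141 |
| 0.20 | 0.738 | 0.623 | 0.469 | 0.265 |
| 0.30 | 0.882 | 0.783 | 0.623 | 0.374 |

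Both p and q are assumptions. The table shows only how the effect would scale.

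**The case against.** The best defence is that little is truly lost.

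- **The scores are kept.** SAP 11.9 tabulates and lists them, and diameters, bleeding and fluid loss are also recorded. This stands. The loss is from the AE tables, not from the study report.
- **Examination findings are a second route.** Physical examination changes are themselves a primary endpoint, and SAP 11.6 can turn them into AEs. This stands in part, for the timing reason in step 2.
- **Stopping rules do not hang on the AE list alone.** A reader might infer that such reactions are invisible to them. The documents do not support that. Protocol 9.2.1, 9.2.3.1 and 9.2.3.2 also count physical examination abnormalities, and the triggers for serious events and hypersensitivity are worded separately. What remains is narrower: several criteria count CTCAE grades, and an unlisted reaction has no planned grade.
- **Pain is not shown to be exempt.** A reader might argue that pain has no diameter and so is always under 10 mm. That does not follow. The sentence just before the rule limits measurement to three visible signs, and the natural reading is that the limit applies to those. Pain would then stay under 11.14.1. The text does not settle this, so it is an ambiguity and not an established exclusion.
- **The timing mismatch is minor.** Subjects are confined until after the 48-hour draw (Protocol 11.2) and monitored throughout (11.9), so an unscheduled observation could settle duration. It is a reason to tie the rule to a scheduled check, not a defect of its own.

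**Conclusion.** The point holds in a limited form. By its wording, Protocol 11.9.7 keeps measured reactions under 10 mm that last 24 hours or less off the AE list whatever their score. Score 2 reactions, and score 3 reactions that qualify on symptoms, can therefore miss the summaries behind the primary endpoint, contrary to 11.14.1. The status of pain or bruising without a measured diameter is unclear.

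It would go too far to say that severe reactions in general drop out. Necrosis or ulceration would be expected to last beyond 24 hours and so be listed; that is a clinical expectation, not something the documents state. It would also go too far to say that each exclusion costs 16.7 points of overall AE incidence, given the condition in step 4.

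The loss is partial and cannot be sized from the documents. The correction is worth making because it is cheap and the affected summary is primary.

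**What to change.** Amend the listing rule in Protocol 11.9.7 so that:

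1. Only score 1 reactions with a measured diameter under 10 mm that are no longer present at the 24-hour evaluation are exempt from AE listing.
2. Any reaction scored 2 or 3 is listed as an AE regardless of size or duration.
3. Symptoms without a measured diameter, such as pain, follow the general definition in 11.14.1.

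This keeps the evident purpose of the exemption and ties persistence to a check that is already scheduled. It still departs from 11.14.1 for mild marks, so 11.14.1 should refer to the exemption. The change affects recording only. Its cost is a short text amendment and a few more AE records.

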11.10 Management of Infusion-Related Reactions and Other Emergency Events

Subjects will be closely monitored by a medical team during drug infusion and in the hours following the end of infusion, for the presence of symptoms of infusion-related reactions (IRR). Subjects will be also encouraged to quickly report any symptoms at any time they occur during the confinement.

If a subject experiences an IRR during study drug infusion, the infusion should be stopped and the subject's condition should be evaluated by a physician. The physician may decide to restart the infusion if the signs and symptoms have resolved. If the infusion is slowed, the total infusion time should not exceed 3 hours (\pm 10 minutes). The study drug should be stopped if the infusion reaction recurs.

The necessary rescue material, equipment and appropriate medications will be available in the clinic to allow rapid intervention in case of emergency including, but not limited to:

- oxygen
- epinephrine for i.v. or endotracheal injection
- antihistamines

- corticosteroids
- i.v. infusion solutions, tubing, catheters, and tape

The following procedures will be followed in the event of a suspected anaphylactic reaction during study drug infusion:

- Stop the study drug infusion.
- Disconnect from the cannula and aspirate 10 mL blood from the dosing cannula if the infusion is to be ceased immediately.
- Maintain an adequate airway.
- Administer antihistamines, epinephrine, or other medications as required by subject status and directed by the Investigator.
- Continue to observe the subject and document observations.

11.11 Study Exit Procedures and ET

Complete physical examination, hematology, biochemistry, coagulation, urinalysis, vital signs (BP, HR, RR, and OT), S-STS, ECG, and AE monitoring, as well as collection of PK, PD, and immunogenicity samples, will be performed on the last study visit (Day 60 ± 3). If not possible, all efforts will be made to complete study exit procedures within 14 days after the last participation of the subject in the study.

11.12 Data Collection and Evaluation

The electronic source data capture system is the primary data collection instrument for the study. Collection screen in the electronic source data capture system will be utilized for the collection of all data. Data will be entered using the English language and should be kept current to enable the monitor to review the subjects' status throughout the course of the study.

Source data should be ALCOA-C (attributable, legible, contemporaneous, original, accurate, and complete). Source documents will be maintained in order to maintain data integrity. The Investigator and/or the clinical staff have the responsibility of ensuring the accuracy, completeness, legibility, and timeliness of the source data.

Details on the data management process will be described in a data management plan (DMP).

11.13 Subject Withdrawal and Replacement

Subjects will be advised that they are free to withdraw from the study at any time. Over the course of the study, the Sponsor and the Investigator or designee may withdraw any subject from the study for one of the reasons described below; subject withdrawal will be done in accordance with the clinical site's SOP:

- Safety reason;
- Non-compliance with protocol requirements;
- Significant protocol deviation;

• Positive alcohol breath test, or drug screen.

Hematology, biochemistry, coagulation, and urinalysis results will be reviewed by the Investigator or designee prior to the infusion; subjects will be withdrawn from the study if it is deemed that the subject's safety may be at risk on the basis of these test results.

Subjects who withdraw, or are withdrawn, from the study for safety and tolerability reasons after dosing will not be replaced. However, subjects who withdraw or are withdrawn from the study after dosing for reasons other than safety and tolerability, may be replaced after consultation between the SRC members. The total number of subjects dosed (including potential replacement subjects) will remain within a maximum of 10 subjects per cohort.

Subjects who withdraw or are withdrawn will be asked to remain at the clinic until the Investigator or designee agrees that the subject is fine and can be discharged. As soon as subject withdrawal is confirmed, blood sampling will be stopped. A PK blood draw may be collected at the time of withdrawal if deemed required by the Investigator. Study exit procedures will be performed at the time of withdrawal from the study or as soon as possible thereafter.

11.14 Adverse Events

11.14.1 Definition of Adverse Event

An AE is defined as any untoward medical occurrence in a patient or clinical trial subject administered a pharmaceutical product and which does not necessarily have a causal relationship with the treatment. An AE can, therefore, be any unfavorable and unintended sign (including an abnormal laboratory finding, for example), symptom, or disease temporally associated with the use of a medicinal (investigational) product, whether or not considered related to the medicinal (investigational) product.

11.14.2 Recording of Adverse Events

AEs will be recorded and evaluated for their seriousness, severity, and relationship to the study medication. AEs will be collected and documented from signing of ICF and throughout the course of the study. For a period of 60 days following the study treatment administration, AEs will be also documented, if reported. AEs will be followed-up until complete resolution, or until the Investigator judges it to be safe to discontinue follow-up. The relationship to the study treatment will be classified according to the clinical site SOPs.

11.14.3 Assessment of Severity

The severity of AEs will be graded according to criteria from the CTCAE (current version 5.0).

The CTCAE displays Grades 1 through 5 with unique clinical descriptions of severity for each AE based on this general guideline (Table 14):

Table 14. Common Terminology Criteria for Adverse Events

GRADE	DESCRIPTION
Grade 1	Mild; asymptomatic or mild symptoms; clinical or diagnostic observations only; intervention not indicated.
Grade 2	Moderate; minimal, local or non-invasive intervention indicated; limiting age-appropriate instrumental activities of daily living (instrumental activities of daily living refer to preparing meals, shopping for groceries or clothes, using the telephone, managing money, etc.).
Grade 3	Severe or medically significant but not immediately life-threatening; hospitalization or prolongation of hospitalization indicated; disabling; limiting self-care activities of daily living (self-care activities of daily living refer to bathing, dressing and undressing, feeding self, using the toilet, taking medications, and not bedridden).
Grade 4	Life-threatening consequences; urgent intervention indicated.
Grade 5	Death related to AE.

11.14.4 Assessment of Relationship to Study Drug

Each AE must be classified based on medical judgment and according to the following relationship categories: probable, possible, remote/unlikely, and unrelated. The definitions for the relationship categories are as follows (Table 15):

Table 15. Description of Adverse Event Relationship Categories

Category	Description
	This category applies to AEs that are considered, with a high degree of certainty, to be related to the investigational product. An AE may be considered probable, if:
	1. It follows a reasonable temporal sequence from the administration of the drug.
Probable	2. It cannot be reasonably explained by the known characteristics of the participant's clinical state, environmental or toxic factors or other modes of therapy administered to the participant.
	3. It disappears or decreases on cessation or reduction in dose (there are important exceptions when an AE does not disappear upon discontinuation of the drug, yet drug relatedness clearly exists; e.g. (1) bone marrow depression, (2) tardive dyskinesias).
	4. It follows a known pattern of response to the suspected drug.
	5. It reappears upon re-challenge. [Related] Possible (must have first two points)
	This category applies to AEs in which the connection with the investigational product administration appears unlikely but cannot be ruled out with certainty. An AE may be considered possible if, or when:
Possible	1. It follows a reasonable temporal sequence from the administration of the drug.
	2. It may have been produced by the participant's clinical state, environmental or toxic factors, or other modes of therapy administered to the participant.
	3. It follows a known pattern of response to the suspected drug.

Category	Description
	In general, this category is applicable to an AE that meets the following criteria:
	1. It does not follow a reasonable temporal sequence from the administration of the investigational product.
Remote/Unlikely	2. It may readily have been produced by the participant's clinical state, environmental or toxic factors, or other modes of therapy administered to the participant.
	3. It does not follow a known pattern of response to the suspected drug.
	4. It does not reappear or worsen when the investigational is readministered.
Unrelated	This category is applicable to AEs that are judged to be clearly and incontrovertibly due only to extraneous causes (disease, environment, etc.), and do not meet the criteria for medication relationship listed under remote, possible, or probable.

